Study Protocol and Statistical Analysis Plan  
For Research Project:

“Cluster-randomized Controlled Trial Examining the Effectiveness of Mindfulness-Based Cognitive Therapy for Anxiety and Stress Reduction within College Students”

clinicaltrials.gov #

conducted by [name], Ph.D.

July 18, 2023

**“Cluster-randomized Controlled Trial Examining the Effectiveness of Mindfulness-Based Cognitive Therapy for Anxiety and Stress Reduction within College Students”**

**Abstract:** The objective of this project is to understand the potential effectiveness of a 4 week Mindfulness-Based Cognitive Therapy intervention delivered using a smartphone application for reducing anxiety and stress within college students. Although in-person mindfulness-based cognitive therapy approaches have been found effective for reducing anxiety and stress; given the pervasiveness of anxiety and stress in this population, there is a need to provide alternative and accessible interventions to improve students' mental health. One such approach may be by leveraging existing tools such Sanvello — a free mindfulness-based cognitive therapy smartphone application — which could more easily be deployed across a broader population. Accordingly, using a cluster-randomized controlled design, this intervention will assess the extent to which 4-weeks of using the Sanvello application was effective for reducing anxiety and stress within college students.

**Aims:**

- 1) To provide an assessment of the efficacy of the Sanvello application for reducing trait-level anxiety.
- 2) To provide an assessment of the efficacy of the Sanvello application for reducing chronic perceptions of stress.

**Number of subjects:** 314 individuals enrolled in a predominately freshman level college course.

**Design:** Cluster-randomized positive control Phase 2 clinical trial.

**Interventional Study Model:** Parallel — Participants are assigned to one of two groups in parallel for the duration of the study.

**Study Population:** The sample consisted of individuals ages 17 to 42 (inclusive) years of age enrolled in a predominately freshman level college course in the mid-Michigan, USA area.

**Eligibility Criteria:**

*Criteria for inclusion:* All individuals enrolled in the course that agreed to participate were enrolled. No individual was turned down due to sex, race, or ethnicity.

*Exclusion criteria:* The following exclusion criteria exist for all participants:

- a. Lack of consent.
- b. Complete inattendance in the college course during the pretest assessment and intervention period.

**Recruitment:** All participants in the course completed either the intervention or control as a course activity. Students had the ability to opt out of their data being used for research purposes.

**Protocol:** This investigation was approved by the Michigan State University Human Research Protection Program.

*Pretest:* Following consenting/opting out of their data being used for research purposes, students completed a series of questionnaires. Each section of students was randomly assigned using a serial stratification approach to either the active experimental group or the control experimental group.

*Experimental arm.* The active experimental group received a mindfulness based cognitive therapy through the Sanvello smartphone application. Participants were encouraged to practice mindfulness daily through the application program "Braving Anxiety," which consisted of 35 modules. The anxiety management program consists of 1) Watch, 2) Read, 3) Listen, 4) Plan, 5) Listen – Mindfulness practice.

*Positive Control arm.* The control experimental group received training on the utilization of mindfulness-based stress reduction breathing techniques. Participants were instructed to set a timer for 5 minutes in order to engage in mindfulness breathing. Comprehensive instructions were provided during the initial laboratory time, elucidating the method by which participants were to direct their attention towards their breath. Moreover, participants were encouraged to cultivate a non-judgmental attitude when confronted with potential distractions and to subsequently redirect their focus back to their breathing. Participants were advised to integrate this technique into their daily lives as a means to alleviate anxiety and stress.

*Intervention.* Participants were instructed to practice mindfulness daily using their instructed approaches for a period of 4 weeks.

*Posttest:* At the end of the 4 week study period, participants completed the same measures as were completed at the start of the study.

**Primary Measures:**

*State-Trait Anxiety Inventory:* Trait anxiety was assessed using the trait component of the Spielberger State-Trait Inventory (STAI) (Spielberger et al., 1970). The questionnaire comprised twenty statements assessing how individuals "generally feel." Participants rate their responses to each question on a 4-point Likert scale, with 1 corresponding to "not at all" and 4 indicating "very much so." Positively oriented questions that do not indicate anxiety, such as "I feel calm," are reverse scored. The possible trait anxiety scores range from 20 to 80, with scores above 45 reflecting high trait anxiety levels (Kayikcioglu et al., 2017).

*Perceived Stress Scale:* Chronic stress was assessed using the Perceived Stress Scale-4 (PSS-4) (Cohen et al., 1983). The questionnaire consisted of four items to capture the frequency of stress-related thoughts and feelings experienced over the past month. The possible scores range from 0 to 16, with higher scores indicating higher perceived chronic stress levels.

**Aims Assessment:**

- 1) *To provide an assessment of the efficacy of the Sanvello application for reducing trait-level anxiety.*

This aim was satisfied by examining intervention (active vs positive control) by time (pretest vs posttest) interactions for the Trait component of the Spielberger State-Trait Inventory.

- 2) *To provide an assessment of the efficacy of the Sanvello application for reducing chronic perceptions of stress.*

This aim was satisfied by examining intervention (active vs positive control) by time (pretest vs posttest) interactions for the *Perceived Stress Scale*.

**Statistical Analysis Plan:**

Data will be analyzed using multi-level modeling as this approach is robust to unbalanced data (i.e., missing observations if any occur) and accounts for a number of sources of variability. Analyses will be conducted with  $\alpha = 0.05$  and Benjamini-Hochberg false discovery rate control = 0.05 for post-hoc decompositions. Dependent variables from each primary outcome will be separately assessed using a 2 (Intervention: active, positive control)  $\times$  2 (Time: pre-test, post-test) univariate multi-level model including the random intercept for Participant, Cluster, and Participant by factor interactions if appropriate.

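### The primary Intervention × Time test has no section × time random effect, so its false-positive rate exceeds 5% if section effects shift over the 4 weeks

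*Combined protocol and SAP*

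**What the plan says.** Under Protocol, Pretest, the unit of allocation is the course section: "Each section of students was randomly assigned using a serial stratification approach" to one of the two arms. The number of sections is not given, and the stratification method is not explained. The sample is "314 individuals enrolled in a predominately freshman level college course".

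Aims Assessment defines the trait-anxiety test as "examining intervention (active vs positive control) by time (pretest vs posttest) interactions for the Trait component", with the same wording for perceived stress. The Statistical Analysis Plan puts this into a 2 × 2 model: "Dependent variables from each primary outcome will be separately assessed using a 2 (Intervention: active, positive control", by two times. It describes the random part as "including the random intercept for Participant, Cluster, and Participant by factor interactions if appropriate". No section × time term is named, and no rule for degrees of freedom is given. Nor does any section set a common pretest mean or use the pretest as a covariate.

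**The concern.** With one pretest and one posttest score per student, the interaction on complete data is the difference between arms in mean change. Anything constant within a section over time drops out of that contrast, and this includes the section intercept. The section-level variation that remains is the shared change from pretest to posttest, and the model has no term for it.

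The participant interactions cannot fill the gap. A participant × time effect cannot be separated from residual error when there is one score per time, and it is independent between students. A participant × intervention effect cannot be estimated because each student is in one arm.

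So the plan allows for clustering in the level of the scores but not in the quantity tested. If sections drift differently over the 4 weeks, the standard error of both primary tests is too small and the nominal 5% error rate is not kept.

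A lesser question is precision. The model estimates a pretest arm difference that random assignment makes zero in expectation, so some pretest information may go unused.

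**Working it through.** **Inputs.** From the documents: N = 314, α = 0.05, one score per time, sections randomised. There is no sample-size calculation to reproduce. Assumed: K = 8, 12 or 16 equal sections split evenly between arms; complete data; a two-sided test; variance 1 at each time; within-section pre-post correlation r = 0.7; ICC 0.01 to 0.05; section-effect correlation c = 0.6 (shifting) or 1 (stable).

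**Main check: false positives without section × time.** Let m = 314/K.

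- Variance of the section change effect: 2 × ICC × (1 − c).
- Variance of a student's change within section: W = 2(1 − ICC)(1 − r).
- True variance of a section's mean change, times m: B = m × 2 × ICC × (1 − c) + W.
- What the planned model uses instead, pooled over 314 − 2 = 312 df: D = [(K − 2)B + (314 − K)W]/312.
- False-positive rate: 2[1 − Φ(1.96/√(B/D))].

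At ICC 0.05, K = 8, c = 0.6: m = 39.25, W = 2 × 0.95 × 0.3 = 0.570, B = 39.25 × 0.040 + 0.570 = 2.140 and D = (6 × 2.140 + 306 × 0.570)/312 = 0.600. Then B/D = 3.57, 1.96/1.89 = 1.04, and the rate is 30%.

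| ICC | B/D at K = 8 / 12 / 16 | False positives |
|---|---|---|
| 0.05 | 3.57 / 2.68 / 2.24 | 30% / 23% / 19% |
| 0.02 | 2.03 / 1.67 / 1.50 | 17% / 13% / 11% |
| 0.01 | 1.51 / 1.34 / 1.25 | 11% / 9% / 8% |

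At c = 1 the section change variance is 0, so B = D = W and the rate is 5% for every K and ICC.

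**Cost of the remedy.** On K − 2 df the critical value is 2.45, 2.23 or 2.14 with 8, 12 or 16 sections, against 1.96. Take a 0.3 SD effect with stable sections and ICC 0.05. The planned test has SE = √(4 × 0.570/314) = 0.0852, 0.3/0.0852 = 3.52, and power Φ(3.52 − 1.96) = 94%. With section × time estimated by REML and t on K − 2 df, simulation (4,000 trials per scenario) gives 79%, 87% and 88%. If c = 0.6, power for the same test is 34%, 46% and 58%. Its simulated false-positive rate is 1.2% to 4.8% across 8 to 16 sections.

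**Secondary check: common pretest mean.** R is the pre-post correlation of section means: R = [ICC × c + (1 − ICC)r/m]/[ICC + (1 − ICC)/m]. With known components and equal SDs the variance falls by (1 − R)/2. For stable sections at ICC 0.05, R = 0.90, 0.87 and 0.85 with 8, 12 and 16 sections, so the ceiling is 5%, 6% and 7%. The table gives the simulated change in variance with components estimated and separate pretest and posttest residual variances. Positive values are gains.

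| Section effects | Posttest/pretest SD ratio | K = 6 | K = 8 | K = 12 | K = 16 |
|---|---|---|---|---|---|
| Stable | 1.0 | 0% | 2% | 5% | 6% |
| Stable | 1.1 | −9% | −5% | −4% | 0% |
| c = 0.6 | 1.0 | not run | 12% | 15% | 13% |

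**The case against.** The strongest defence of the plan is that it does recognise clustering, and that an Intervention × Time interaction is a conventional primary test that matches the aims. If section effects are stable over 4 weeks, the omission does no harm. The remedy then costs 6 to 15 points of power and can be conservative, with false positives as low as 1.2%. No documented figure shows that section effects move, and every input except N is assumed. Much of the protocol is also in the past tense, so the analysis may already have been run.

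The power cost and the missing inputs stand, and both must be stated. They do not justify a test whose validity depends on section effects being stable, because the documents do not address that condition and the model cannot detect a departure from it.

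Three stronger readings might be inferred, and the documents support none of them.

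- *The plan ignores clustering.* It does not: a Cluster random intercept is named.
- *The trial's false-positive rate is 30%.* That is one corner of an assumed grid, and the rate is 5% with stable sections.
- *The free pretest difference is an error that wastes 5% to 20% of the variance.* Under randomisation the planned estimator is unbiased. The 5% to 20% range is (1 − R)/2 for R from 0.9 to 0.6 with known components and equal SDs. At r = 0.7 and ICC 0.05 with stable sections, the realistic gain is 0% to 6%. It becomes a loss with few sections or a larger posttest SD.

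The common mean also needs pretest scores and exclusions that do not depend on arm. The protocol says "Following consenting/opting out of their data being used for research purposes, students completed a series of questionnaires" before it mentions assignment, but it does not state that order outright. The attendance exclusion extends into the intervention period, and the allocation method is undefined.

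**Conclusion.** The main point holds: the random-effects structure as written is wrong for a section-randomised trial whose primary test is a comparison of changes. The consequence is conditional. With shifting section effects (c = 0.6, r = 0.7) the error rate runs from about 8% (16 sections, ICC 0.01) to about 30% (8 sections, ICC 0.05). With fully stable section effects it is 5%. It applies to both primary outcomes. The size rests on equal sections, an even split, complete data and equal pretest and posttest variances.

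The common-pretest-mean model is a matter of precision only and is optional. Its gain is about 0% to 6% of the variance with stable section effects and equal SDs, 12% to 15% with 8 to 16 sections if section effects change substantially, and possibly negative. The gain may differ by outcome. Stress is measured thus: "The questionnaire consisted of four items to capture the frequency of stress-related thoughts and feelings experienced over the past month". Trait anxiety uses twenty statements about general feelings. A lower pre-post correlation for stress is plausible but is an assumption.

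**What to change.** In the Statistical Analysis Plan, for both primary outcomes:

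1. Add a section × time random effect to the 2 × 2 model. Test Intervention × Time on section-based degrees of freedom: the number of sections minus 2, fewer if strata are modelled.
2. State the number of sections and the size of each, explain the stratified allocation, and report the estimated section and section × time variances.
3. Optionally, report a model with a common pretest mean and separate pretest and posttest residual variances, labelled as supporting. It should carry the same section × time term. Do this only if the pretest preceded knowledge of assignment and exclusions did not depend on arm; the plan should say whether both held. The planned interaction, with item 1 added, stays primary.

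If outcomes have already been analysed, rerun the primary tests with item 1, report both results, and date the change.

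The cost is a few lines of text and no new data. Item 1 brings the wider reference distribution and the loss of power shown above if section effects are stable. Item 3 can lose precision, for example about 9% of the variance with 6 stable sections and a posttest SD 10% larger.

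### Does the plan need a rule for its combined anxiety-and-stress objective when only one of the two primary outcomes is significant?

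*Combined protocol and SAP*

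**What the plan says.** The Abstract is worded in the singular: "The objective of this project is to understand the potential effectiveness" of a four-week intervention "delivered using a smartphone application for reducing anxiety and stress within college students". Its last sentence says the trial will "assess the extent to which 4-weeks of using the Sanvello application was effective for reducing anxiety and stress within college students".

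The Aims section then lists two unranked aims, "To provide an assessment of the efficacy of the Sanvello application for reducing trait-level anxiety" and "To provide an assessment of the efficacy of the Sanvello application for reducing chronic perceptions of stress". Aims Assessment ties each aim to one contrast. For anxiety it reads "This aim was satisfied by examining intervention (active vs positive control) by time (pretest vs posttest) interactions for the Trait component", and the same construction is used for the Perceived Stress Scale.

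The Statistical Analysis Plan fits one multi-level model per outcome ("Dependent variables from each primary outcome will be separately assessed") with α = 0.05. Its only multiplicity step is "Benjamini-Hochberg false discovery rate control = 0.05 for post-hoc decompositions", which does not reach the two interaction tests. No section calls the outcomes co-primary or alternative, and none says what a split result means for the Abstract's combined wording.

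**The concern.** Two outcomes are joined by *and* in the objective but tested one at a time. If the anxiety interaction is significant and the stress interaction is not, one author could write that the app reduces anxiety and stress, and another that it reduces anxiety only. The plan has no sentence that chooses between them. Aims Assessment does not help here: an aim that is met by examining an interaction is met whatever the result.

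A split result is not a remote possibility. If both effects are real and each test has 80% power, exactly one test is significant in 14% to 32% of trials, depending on the correlation. What is at stake is the wording of the headline conclusion, above all when the app truly helps one outcome only.

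**Working it through.** The plan states no power, correlation or family-wise error, so there is no figure of its own to reproduce.

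**Inputs.** From the SAP: two primary outcomes, separate models, α = 0.05. Assumed, because the plan does not give them:
- two-sided tests that hold their nominal level;
- 80% power for a real effect, so mean z = 1.960 + 0.842 = 2.802;
- bivariate normal test statistics with correlation r from 0 to 0.8.

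Success on an outcome is z > 1.960 in favour of the app, with probability 0.025 under no effect and 0.80 under a real effect.

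**At r = 0, by hand**
- Helps one outcome only. Either suffices: 1 − (1 − 0.80)(1 − 0.025) = 0.805. Both needed: 0.80 × 0.025 = 0.020.
- Helps neither. Either: 1 − 0.975² = 0.0494. Both: 0.025² = 0.0006.
- Helps both. Either: 1 − 0.20² = 0.96. Both: 0.80² = 0.64. Exactly one: 2 × 0.80 × 0.20 = 0.32.

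**Over r, by bivariate normal integration.** P(both) is the joint upper-tail probability; P(either) = p₁ + p₂ − P(both); P(exactly one) = p₁ + p₂ − 2P(both).

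| Truth | Event | r = 0 | r = 0.5 | r = 0.8 |
|---|---|---|---|---|
| One real | either | 0.8050 | 0.8003 | 0.8000 |
| One real | both | 0.0200 | 0.0247 | 0.0250 |
| Neither real | either | 0.0494 | 0.0454 | 0.0390 |
| Neither real | both | 0.0006 | 0.0046 | 0.0110 |
| Both real | either | 0.9600 | 0.9128 | 0.8710 |
| Both real | both | 0.6400 | 0.6872 | 0.7290 |
| Both real | exactly one | 0.3200 | 0.2257 | 0.1419 |

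At other powers, exactly one is significant in 50% to 20% of trials (50% power) or 18% to 9% (90% power) as r goes from 0 to 0.8.

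**What the 80% measures.** In the one-real row, P(either) = 0.80 + 0.025 − P(both). Since P(both) lies between 0.020 and 0.025, the result lies between 0.805 and 0.800. It is the assumed power plus at most half a percentage point. With 50% power it would be about 50%. It says that a true single effect is usually detected, and it measures no inflation of a test.

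**The same case reported aim by aim.** The affected outcome's aim is supported with probability 0.80, correctly. The unaffected outcome's aim is wrongly supported in favour of the app with probability 0.025, for every r. No statement is left to which the 80% applies as an error.

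**Would multiplicity control help?** Suppose the Benjamini-Hochberg step were applied to the two interaction p-values. Something is then declared significant in favour of the app if its p ≤ 0.025, or if both p ≤ 0.05. Power at 0.025 is P(Z > 2.241 − 2.802) = 0.712. By simulation, either-outcome success with one real effect is about 72% at r = 0 and 71% at r = 0.8. The figure falls only from about 80%, because the difficulty would be one of wording and an adjusted threshold does not act on wording.

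**The case for a change.** The best case for acting is that two aims tested at 0.05 settle what may be said about each aim, but not what may be said about the Abstract's objective. Nothing links the two results back to it, no success criterion is given, and three sentences in the SAP would close the gap at no statistical cost. There is also a plain multiplicity point: with neither effect real, at least one of the two tests is significant in some direction with probability 1 − 0.95² = 0.0975 at r = 0, falling to 0.0781 at r = 0.8.

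The textual part stands: no rule for a split result is written anywhere. The inference from it is weak. The Abstract speaks of an extent and of potential effectiveness, in a trial labelled Phase 2. That is graded language and does not define a pass-or-fail joint claim. Treating it as a single dichotomous conclusion, and then computing how often it is wrong, attributes to the plan a decision that it does not make. The sections that do specify inference all run outcome by outcome.

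The multiplicity figure is correct, but it describes the chance of at least one false result across two distinct questions. With a separate aim for each, 0.05 per aim is a defensible choice, and each claim keeps its nominal error. Requiring both outcomes for a joint claim would have a price: with both effects real, it is reached in 64% to 73% of trials, against 96% to 87% if either were enough.

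**Conclusion.** No change is needed. The plan omits a sentence that its own structure supplies: two aims, two interactions and two models lead to two conclusions, each at 0.05. A competent analyst facing a split result would report the outcome that moved and say that the other did not, and a reader shown both interactions could see the same. The contrast of about 80% against 2.0% to 2.5% arises only if one significant outcome is taken to support a claim about both, which no section allows and which the word *and* argues against.

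A clarifying sentence would do no harm, but it would restate the existing structure and leave every p-value, the alpha, the sample size and the data as they are. Aims Assessment is written in the past tense, so the analysis may already be done, which lowers the value of an addition further.

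This conclusion assumes that each interaction test holds its nominal level; the number of course sections is not given, and that is a separate question. The sizes quoted depend on the assumed power and correlation. The conclusion does not, because the false-claim rate per aim is unaffected by either.
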